Given the complexity and highly subjective nature of the outcome of participation, particularly when occurring in the community¹¹, selecting pragmatic individual-based approaches that reflect and account for real-world clinical settings (e.g., variability of participants, their participation preferences/choices and their environmental characteristics) is critical¹². **This pilot study** will therefore employ a replicated individual-based multi-baseline experimental design across youth, termed Interrupted Time Series (ITS)¹³. In this design, the time-point in which the intervention is introduced for each youth is varied, and each youth serves as a unit of analysis and acts as its own control. By varying the baseline lengths across participants, extraneous variables are controlled for, which in turn strengthens the internal validity of the study allowing us to conclude with greater confidence that change in participation levels and body functions is due solely to the intervention. To further increase internal validity and to minimize potential bias, each youth is randomly assigned to the order (timing) of the intervention.

Embedded in Comparative Effectiveness Research (CER)¹² and in ITS designs¹⁴ we aim to achieve a broad and diverse sample of youth, as this provides an opportunity to replicate the intervention effect across different circumstances/environmental characteristics/community settings and, consequently, further supports the generalizability of results. ITS design is particularly relevant when targeting children with physical disabilities (e.g., CP) in which the variability in functioning is large¹⁵. It allows for heterogeneity within the studied sample and accommodates for complex cases, which is beneficial and meaningful in rehabilitation, as opposed to traditional Randomized Controlled Trials that employs strict exclusion criteria limiting the applicability of the findings to the clinical setting/reality. Furthermore, having a diverse sample allows for a better understanding of for whom and under what conditions the intervention is most and least effective – an important element of CER that can better inform clinical decision-making.

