weeks. A 6-week intervention will then be implemented for each participant. Four outcome measures will be monitored weekly throughout the three phases of the study: baseline, intervention and follow up (week 16 and 18). Figure 1 illustrates the ITS design across 4 participants; it will be replicated 2 times resulting in the examination of 8 participants. Three body functions: motor, cognitive and affective will be measured weekly, resulting in 3 individual trajectories of change – each based on 18 equally-spaced data points. The performance of each activity will also be monitored weekly using the performance scale of the COPM – a 10-point scale that is valid, reliable and sensitive-to-change²⁶. This will result in 24 trajectories of change in body function (8 participants X 3 body functions) and 8 additional trajectories illustrating change in performance in the actual activity (8 participants X 1 activity). Thus, a total of **32 trajectories**, 4 per participant, representing 8 profiles of change will be plotted and analyzed. A combination of 8 cases measured on 18 occasions allows us to estimate the overall effectiveness of the intervention (Aim 1) as well as to determine aspects of feasibility and applicability (e.g., duration of intervention, optimal number and intervals of data points, etc) of this design (Aim 2) and assist in calculating a sample size for a larger clinical trial (Aim 3)³¹.

Figure 1 - Study Design

A kit of outcome measures to assess body functions

A kit of 5 measures will be available to assess motor, cognitive and affective body functions over time. Based on the task analysis, the therapist and youth will select one aspect of each body function (3 total) required to complete the chosen activity, while considering the existing impairments and strengths of the youth; 4 options of assessments will be available for the **motor** aspect and a single tool for both **cognitive and affective** functions with multiple sub-scales for

each function. The therapist will match the assessment including specific sub-scales to the identified body functions by drawing on the ICF linking rules²⁹. If more than one component of a specific body function is identified, the most impaired one will be selected by the youth.

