Assessors, independent of the intervention, will administer the assessments every week at the youth's home (30-60 min). They will be blinded to the time point in which the intervention begins and to the actual chosen activity/program.

To measure the **affective** (e.g., anxiety, social stress, self-esteem), and **cognitive** (e.g., attention problems, learning problems) aspects of body function, the self-report form or parent form of the **BASC-2** will be used, depending on the youth's ability. The **BASC-2**, completed in 15-30 minutes, is a valid and reliable 4-point scale for evaluating behavior and self-perception of children; such as externalizing and internalizing problems, behavioral symptoms and adaptive skills/personal adjustment³².

To measure **motor-related** body functions, four measures can be used: the **SAROMM**, the **TIS**, the **FRT** and the **Jamar dynamometer**. The **SAROMM** is administered by a trained rater and requires 15 to 30 minutes to complete; it measures active/passive range of motion of lower and upper extremities as well as spinal movements using a 5-point scale. The **SAROMM** has demonstrated good inter-rater and test-retest reliability (>.80) as well as sufficient construct validity³³. The **TIS** assesses trunk control and includes 3 sub-scales; static sitting balance, dynamic sitting balance and coordination, and is administered in less than 20 minutes. It contains 17 items rated on a 2-, 3- or 4-point scale. Total score ranges from 0 (low performance) to 23 (high performance). The **TIS** was found to be reliable and valid among youth with CP³⁴. The **FRT** assesses the maximum distance in inches the participant can reach forward while standing/sitting in a fixed position. It is a reliable, valid and responsive tool³⁵ and takes 5 minutes to administer. The **Jamar dynamometer** measures grip strength; scores range from 0 to 200 pounds of force and normative data has been established for youth³⁶.

All scores will be converted to z-scores based on available data of standard deviations and mean scores of this population; this will allow for comparison across trajectories and the examination of the overall effect of the intervention statistically (Aim 1).

Anticipated output #1: A significant change in at least 2 of the 3 body functions will be observed in 6 of the 8 participants (75%) following the intervention.

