The two experts will independently conduct a systematic classification process¹⁷. Each expert will detect similarities and differences in patterns of change within each case using Hawkins et al.³⁷ guidelines. In this process, cases will be clustered based on aspects of change that reflect the extent of the intervention effect. Examples include: number of replicated effects across body function and level and trend of change. Once an agreement is reached and clusters are formed, group members/cases will be described in terms of age, sex, income, the characteristics of the community-based activity programs, the length, intensity and activity type (based on the therapist's structured form) as well as functional issues (based on assessment of body functions). Such an analysis will allow us to identify the profiles of youth for whom the treatment is more effective and less effective as well as the conditions under which the change is observed or partially observed. Furthermore, this information, analyzed with the input of stakeholders, can inform the design of a larger clinical trial testing this intervention.

Potential Challenges and ways to overcome them

Like in many 'real-life' studies, youth may wish to continue participating in the chosen program beyond the 6-week period or decide to engage in an additional activity simultaneously. Such occurrences will be documented by the therapist and will be incorporated into the analysis. This information will assist in identifying specific circumstances that may influence the results (Anticipated output #3). It is plausible that specific programs prioritized by youth will not be available in their community at a certain time (e.g., seasonal sports). A discussion will take place to identify ways to engage in a similar activity while adhering to the area of interest that was expressed. The therapist will document this process. Additionally, some youth might prefer to start the intervention before completing the assigned baseline period (either 2, 4, 5, or 8 weeks). Through a discussion with the youth and their family, the reason for employing such procedure will be described. Furthermore, during the baseline period, youth are allowed to continue and receiving any ongoing rehabilitation services and this will not be affected by such a delay.

Research team

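### Output #3 reads clusters of observed change among 8 youth as profiles of who benefits, without setting the spread between youth against within-youth noise

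*Combined protocol and SAP*

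**What the plan says.** Under Anticipated output #3, two experts classify the cases independently and then agree. The basis is observed change: "cases will be clustered based on aspects of change that reflect the extent of the intervention effect". The features are illustrative and have no cut-offs: "Examples include: number of replicated effects across body function and level and trend of change". Description follows: "Once an agreement is reached and clusters are formed, group members/cases will be described in terms of age, sex, income", and then programme characteristics, length, intensity, activity type and functional issues, about eight descriptors in all. The conclusion drawn is "Such an analysis will allow us to identify the profiles of youth for whom the treatment is more effective and less effective". The section adds that this information can inform a larger trial.

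The design section on interrupted time series makes the same link: "having a diverse sample allows for a better understanding of for whom and under what conditions the intervention is most and least effective". It ties that understanding to clinical decision-making.

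Two other places deal with variation between participants. Under Anticipated output #1, a mixed-effects hierarchical linear model (HLM) that allows for individual variance is used to estimate the overall effect. Under Scientific Merit, the third aim examines variation within and across participants, for the purpose of sizing a larger study. The output #3 text refers to neither.

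**The concern.** Observed change in one youth is the true effect plus noise from a short weekly series. Eight youth with identical true effects will therefore usually show different numbers of improved functions and different levels and trends. Clusters formed on those differences may reflect noise. Once clusters exist, a handful of descriptors compared across so few cases will often show some contrast.

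Followed as written, output #3 can report such a contrast as a profile of who benefits more or less. It is one of three anticipated outputs and is meant to feed the next trial's design. Expert blinding and consensus reduce rater bias, but they do not separate signal from noise, since two experts can agree on a chance pattern.

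**Working it through.** **Inputs.** Study design: 8 youth ("it will be replicated 2 times resulting in the examination of 8 participants") and 3 body functions each, so 8 × 3 = 24 trajectories. Anticipated output #1: change in at least 2 of 3 functions in 6 of 8 youth, and 6/8 = 0.75, which reproduces the plan's 75%. The plan states no error rate or detection probability for output #3. I treat 0.75 as a response probability common to all youth, and youth as independent.

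**Step 1: split under one common response probability q = 0.75.**

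- Both groups occupied: 1 − q^8 − (1−q)^8 = 1 − 0.75^8 − 0.25^8 = 1 − 0.1001 − 0.00002 = 0.900.
- At least two youth on each side: 0.900 − 8(0.75^7)(0.25) − 8(0.25^7)(0.75) = 0.8999 − 0.2670 − 0.0004 = 0.633.
- Exactly 6 of 8 responding, the result the plan anticipates: 28 × 0.75^6 × 0.25^2 = 0.31.

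So the anticipated 6/2 result is itself quite compatible with no difference between youth.

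**Step 2: dependence on the per-trajectory detection probability p.** With the three functions independent, q = 3p²(1−p) + p³, and q = 0.75 corresponds to p = 0.674. For grouping on the count of improved functions (0 to 3), P(at least two different counts) = 1 − Σ[Bin(3,p) at k]^8. For the 2-of-3 split, the first formula in Step 1 applies.

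| p | At least two different counts | Split on 2 of 3 |
|---|---|---|
| 0.02 or 0.98 | 38% | 1% |
| 0.05 or 0.95 | 71% | 6% |
| 0.10 or 0.90 | 92% | 20% |
| 0.20 or 0.80 | over 99% | 58% |
| 0.50 | over 99% | 99% |
| 0.674 | 99.8% | 90% |

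If the three functions are perfectly correlated within a youth, the split probability is 34% at p = 0.05 or 0.95, 57% at 0.90, 90% at 0.75 and 99% at 0.50.

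**Step 3: simulation check.** Assumptions: 18 weekly points, baselines of 2, 4, 6 and 8 weeks in two blocks, AR(1) errors with correlation 0, 0.3 or 0.5, the same level shift for every youth, detection when z exceeds 1.96, and 1,500 trials per setting. The z rule stands in for visual inspection.

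- No shift: different counts in about 45% of trials; 2-of-3 split in under 2%.
- Shift of 0.5 to 2 SD: different counts in 89% to 100%. The 2-of-3 split ranges from about 24% (0.5 SD) to about 99% (1 to 1.5 SD).
- Shift of 3 SD: different counts in 11% to 31%; 2-of-3 split in under 2%.

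**Step 4: descriptors.** Take a 6/2 split and a binary trait, unrelated to effect, held by 4 of the 8. The two youth in the small cluster match on it (both have it or both lack it) with probability 2 × C(4,2)/C(8,2) = 12/28 = 0.43. With six independent traits of this kind, they match on at least one with probability 1 − (1 − 0.43)^6 ≈ 0.97. This only illustrates how easily a contrast appears, as the plan sets no rule for what counts as one.

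**The case against.** The strongest reply is that this is a pilot. Output #3 is introduced as seeking better understanding, the information is only said to be able to inform a larger trial, and no error-rate claim or go/no-go rule rests on it. That stands, and it limits the stakes. It also argues for hypothesis wording, which the concluding sentence of the section does not use.

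Several stronger readings are tempting, and the documents do not support them:

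- **That spurious profiles appear in most trials, or in at least 63% of them.** The plan gives no detection probability, and Steps 2 and 3 show low figures at the extremes. The 63% is the chance of at least two youth per side at a common 75% rate. It is not a minimum, and it is not the chance of a false profile.
- **That the procedure cannot return a negative answer.** The text is silent on a single cluster or no profile, but silence is not prohibition. The clustering is expert judgement with example features, so nothing says that every difference in count makes a cluster.
- **That variation between youth is never examined.** The HLM and the third aim both bear on it. What is missing is the link to output #3.
- **That a homogeneity test should decide whether profiles may be named.** In the same type of simulation, with mean shift 1.5 SD, autocorrelation 0.3 and error SD and autocorrelation treated as known, a 5% test detected a between-youth SD of 0.5 in about 61% of trials. It would miss real differences in about 39%.

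**Conclusion.** The concern holds in limited form. The output #3 text moves from clusters of observed change to identified profiles without setting between-youth spread against within-youth noise, and the two parts of the plan that could inform that comparison are not connected to it. At the plan's anticipated 75% rate, a response probability shared by all 8 youth still gives a responder/non-responder split in about 90% of trials, and at least two youth per side in about 63%. This rests on reading 6 of 8 as a common probability, on independence between youth, and on grouping by the 2-of-3 criterion. None of it shows that effects are in fact equal, or that any clusters found will be noise. It shows that clusters alone cannot tell the two situations apart. Outputs #1 and #2 are unaffected. The change is worth making because it alters what output #3 can conclude at almost no cost.

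**What to change.** In the Anticipated output #3 section:

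1. Beside the visual clusters, report for each outcome the between-youth SD of the intervention effect from the planned HLM with its interval, the typical within-youth standard error, and the shrunken youth-level effects.
2. Replace the claim that the analysis will identify profiles with a statement that it will generate hypotheses about profiles, and state how many descriptors were compared.
3. Add that when the interval for the between-youth SD includes values near zero, the clusters are case description: the data then do not show that effects differ between youth, nor that they are equal.

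Do not make a significance test the condition for presenting clusters.

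Cost: extra output from a model already planned and a few sentences of text, with no new data, visits or staff. The downside is a weaker output #3 claim, because with 8 youth the between-youth SD will be imprecise and the likely product is a hypothesis.

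### Output #3 uses staying on past week 6, and activities added after the start, to explain response, although staying on may result from response and cannot explain the weeks before it

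*Combined protocol and SAP*

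**What the plan says.** Under Anticipated output #3, grouping starts from the outcome: "cases will be clustered based on aspects of change that reflect the extent of the intervention effect". Once the clusters are agreed, they are described by age, sex, income, programme characteristics (including "the length, intensity and activity type", taken from the therapist's form) and functional issues. The stated purpose is to find the kinds of youth who benefit more or less and "the conditions under which the change is observed or partially observed". The result may inform a larger trial.

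Under Potential Challenges and ways to overcome them, the plan expects that "youth may wish to continue participating in the chosen program beyond the 6-week period or decide to engage in an additional activity simultaneously". It then says: "Such occurrences will be documented by the therapist and will be incorporated into the analysis". The role given to these events is explanatory: "This information will assist in identifying specific circumstances that may influence the results (Anticipated output #3").

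Under Study design, the planned exposure is the same for all: "A 6-week intervention will then be implemented for each participant". Baselines of 2, 4, 6 or 8 weeks are randomly assigned within an 18-week series, with weekly measurement.

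**The concern.** The plan names one direction only, from circumstance to result. Staying on past week 6 comes, by its timing, after about six weeks in the programme, and it is the youth's wish. Youth who feel they are progressing are plausibly the ones who stay. A cluster defined by large change would then contain more continuers even if continuing did nothing.

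Nothing in the plan guards against this. It does not separate items fixed before the programme from choices made during or after it. It does not ask for the date of, or reason for, a choice. It does not say which data points a choice may explain, and it gives no caution on direction.

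What is at stake is the message to the larger trial. Estimating the optimal length and intensity of the programme is a stated aim (Scientific Merit, aim 2). Output #3 could name longer participation as a condition for benefit when benefit led to longer participation.

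**Working it through.** **The plan's own figures.** The plan gives no number for this point. Its neighbouring counts reproduce: 8 × 3 = 24 body-function trajectories, 8 × 1 = 8 performance trajectories, 32 in total; 6/8 = 75%.

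**Step 1: timing.** Inputs from Study design: 18 weekly points, baselines of 2, 4, 6 and 8 weeks, a 6-week programme. Programme end = baseline + 6. Weeks left = 18 − programme end.

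| Baseline (weeks) | Programme ends (week) | Share of series before any continuation | Weeks left |
|---|---|---|---|
| 2 | 8 | 8/18 = 44% | 10 |
| 4 | 10 | 10/18 = 56% | 8 |
| 6 | 12 | 12/18 = 67% | 6 |
| 8 | 14 | 14/18 = 78% | 4 |

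Continuation cannot have caused change in the second column's weeks, yet the clusters are built on the whole trajectory. The weeks available for continuing are set by the randomised baseline, so recorded weeks of participation also partly reflect allocation.

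**Step 2: how often pure reverse direction would look like a condition for benefit.** These assumptions are not in the documents: the four youth with most change are compared with the four with least; half of all youth continue; continuing has no effect on function. A youth continues if r × change + √(1 − r²) × noise > 0, with change and noise standard normal.

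| r | Continue: more-change / less-change cluster | P(more continuers in more-change cluster) | P(at least two more) |
|---|---|---|---|
| 0 | 50% / 50% | 36% | 14% |
| 0.3 | 59% / 41% | 57% | 29% |
| 0.5 | 65% / 35% | 71% | 43% |
| 0.7 | 72% / 28% | 85% | 60% |

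**Step 3: check by hand.** Let X be the continuers in the more-change cluster, Bin(4, p), and Y those in the other, Bin(4, 1 − p), treated as independent. Then X + (4 − Y) is Bin(8, p). More continuers means this sum is at least 5; at least two more means at least 6.

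- p = 0.5: (56 + 28 + 8 + 1)/256 = 93/256 = 36%, and (28 + 8 + 1)/256 = 37/256 = 14%.
- p = 0.65: 0.279 + 0.259 + 0.137 + 0.032 = 0.71, and 0.259 + 0.137 + 0.032 = 0.43.

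Both agree with the simulation.

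**Step 4: a different split.** With 6 responders and 2 non-responders, and assumed continuation of 70% against 30%, the responders show the higher share with probability 0.80. With no relation it is 0.42. The conclusion does not depend on the 4/4 split.

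**The case against.** **Programme length.** A reader might infer that youth choose the length of their programme according to how they are doing. The documents do not say so. Length and intensity are listed with the programme's characteristics, and the therapist's form is introduced under Intervention and Procedure as a record of the programme. Length or intensity set by the provider is not open to this objection. Only realised weeks attended are, where they vary through early stopping or staying on.

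**Added activities.** A reader might also infer that an added activity is a result of response. The plan says only that it runs at the same time, with no date or reason. One begun early could be a genuine co-intervention, and calling it a response would impose the opposite direction with no better evidence. Continuing may likewise truly affect the 10, 8, 6 or 4 later weeks.

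**Cutting the series.** Clustering only on baseline plus programme weeks looks tidy, but it would discard 4 to 10 of 18 points, including the follow-up at weeks 16 and 18. Every series would also end six weeks after the start, which would reveal the start point to experts whom the plan blinds to it (Anticipated output #1).

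**Size and consequence.** The simulation assumes reverse direction, so it cannot show how likely that is here. With no relation at all the pattern still appears in 36% of trials, so part of the problem is simply eight cases. Output #3 is exploratory and cautiously worded, and programme length has other inputs: the output #2 checklist and stakeholder advice.

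All of this stands, and it narrows the point. It does not answer the core: continuation is chosen late, is offered as an explanation of response, and carries no safeguard on direction.

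**Conclusion.** The point holds in limited form. Continuation past week 6, and any activity added after the start, should not be used as conditions that explain clusters formed on the whole trajectory. For continuation the timing argument needs no assumed correlation: 44% to 78% of each series precedes it. This rests on weekly measurement and the 2, 4, 6 and 8-week baselines given under Study design. The potential-challenges section lists 5 in place of 6, which would give week 11 and 7 weeks left for that youth.

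Under the stated assumptions, pure reverse direction puts more continuers in the more-change cluster in 57% to 85% of trials (r = 0.3 to 0.7), against 36% by chance. It puts at least two more there in 29% to 60%, against 14%. These figures show what could happen, not what will.

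A reader might go further and conclude that the profiles will be reversed or that the effectiveness result is compromised. Neither follows. The documents give no data on why youth stay on, and output #1 does not use these descriptors. The consequence is confined to the profiles passed to the larger trial.

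**What to change.** Keep the blinded visual reading and the clustering on the full 18-week series. Then:

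1. Under Anticipated output #3, limit the conditions used to profile clusters to items fixed before the first programme session: youth characteristics, activity type, provider-scheduled length, planned sessions per week and session length.
2. Have the therapist's form record the date of, and reason for, continuation, early stopping and each added activity.
3. Report these in a separate table as post-start events whose direction of effect is undetermined. Relate each only to data points after its date, and treat added activities as possible co-interventions.
4. Show the 10, 8, 6 or 4 post-programme weeks by whether the youth continued or stopped, with the assigned baseline length beside each case.

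The cost is a few sentences of analysis wording and a few form fields. No data are dropped, and blinding and the conduct of the programme are unchanged. The downside is that realised duration is no longer offered as an explanation of response.
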